## Attachments

Attach Type	File Name
ResearchProcedures	Table of Events v1 dated 21 Nov 23 (Clean).pdf
ResearchProcedures	Table of Events v1 dated 21 Nov 23 (HL).pdf

## **Data Collection & Research Materials**

In this section, please provide the following:

- Describe all sources or methods for obtaining research materials about or from living individuals (such as specimens, records, surveys, interviews, participant observation, etc.), and explain why this information is needed to conduct the study.
- For each source or method described, please list or attach all data to be collected (such as genetic information, interview scripts, survey tools, data collection forms for existing data, etc.).
- If you will conduct a record or chart review, list the beginning and end dates of the records you will view.

Either a member of the research team or the participant/LAR will provide the information collected on the following forms. This information is pivotal to our study.

We will collect the following from the participants:

· Demographic information (Name, initials, gender, race, age, study number, mailing address, home phone number, social security number, ID number (if applicable)

· Dates including date of birth, hospital admissions/discharges, study visits

Results of physical exams, EKGs, MRIs, CT imaging, and other diagnostic and medical procedures related to this study

91630

· Medical and medication information related to this study

· American Spinal Injury Association Assessment

- · Spinal Cord Independence Measure
- · ISP, arterial blood pressure, and microdialysis measurements
- · Peripheral nerve tissue

The following data collection forms will be used:

- ASIA-ISCOS Worksheet 10-2019

- SCIM-Spinal Cord Independence Measure vIII

## Attachments

Attach Type	File Name
DataCollection	ASIA-ISCOS-Worksheet_10.2019.pdf
DataCollection	SCIM-SPINAL CORD INDEPENDENCE MEASURE vIII.pdf

### Resources

Describe the availability of the resources and adequacy of the facilities that you will use to perform the research. Such resources may include:

- Staffing and personnel, in terms of availability, number, expertise, and experience;
- Computer or other technological resources, mobile or otherwise, required or created during the conduct of the research;
- Psychological, social, or medical services, including equipment needed to protect subjects, medical monitoring, ancillary care, or counseling or social support services that may be required because of research participation;
- Resources for communication with subjects, such as language translation/interpretation services.

This pilot study will be undertaken with colleagues in the Department of Neurosurgery and at the Spinal Cord and Brain Injury Research Center (SCOBIRC) at the University of Kentucky. As such, our group of investigators will have access to world-class infrastructure and mentorship. Specifically, investigators with experience in sophisticated data analysis will critically contribute to the interpretation of continuous ISP and spinal fluid metabolic measurements. Fortuitously, neurosurgery and neuroscience colleagues at the University of Kentucky have also established and validated a reproducible source of cellular tissue from the peripheral nervous system that contain injured-peripheral nerve tissues shown to include a variety of cells that express several key growth factors and repair molecules. The availability of this validated implantation model bypasses the need for cell culturing and concomitant immunosuppression that introduce significant logistic and safety related considerations; this is especially the case considering the relative immune compromised state and elevated risk of infections in the acute phase after SCI that can independently negatively impact neurological outcomes.

The participants will be followed by [name], PhD his research team, which includes the coordinator, and the professional staff of the spinal cord center. Emergency medical equipment, medications and supplies are available in the hospital and KNI to handle any untoward reaction. This project will utilize the EDT to obtain clinical/claims data associated with the inclusion/exclusion criteria provided in the study design.

#### Potential Risks & Benefits

Risks

- Describe any potential risks including physical, psychological, social, legal, ability to re-identify subjects, or other risks. Assess the seriousness and likelihood of each risk.
- · Which risks may affect a subject's willingness to participate in the study?
- Describe likely adverse effects of drugs, biologics, devices or procedures participants may encounter while in the study.
- Qualitative research describe ethical issues that could arise while conducting research in the field and strategies you may use to handle those situations.
- Describe any steps to mitigate these risks.

### Benefits

- Describe potential direct benefits to study participants including diagnostic or therapeutic, physical, psychological or emotional, learning benefits. This cannot include incentives or payments.
- State if there are no direct benefits.
- Describe potential benefits to society and/or general knowledge to be gained.

Describe why potential benefits are reasonable in relation to potential risks. If applicable, justify why risks to vulnerable subjects are reasonable to potential benefits.

The risks listed are risks associated with the research-only procedures and that risks associated with standard of care procedures will be addressed with the participants in separate discussions with providers/consents/etc.

DMED: The potential risks of DMED relate to exposure of the intradural compartment (opening and closure of the dural membrane) and the midline dorsal myelotomy. Although rare (estimated at < 1%), there is a possibility of intraparenchymal and/or intradural

bleeding with associated neurological worsening. As per standard-of-care guidelines, all participants will be closely monitored in the neurosurgery ICU for any signs or neurological worsening and will undergo further diagnostic imaging as indicated. Despite water-tight closure of the dura with an expansive dural substitute patch, there is also a potential risk of spinal fluik leak and pseudomeningocele formation (estimated risk of 5%). As per standard-of-care guidelines, wound healing will be closely monitored during the post-operative period for any evidence of swelling or abnormal fluid collection.

91630

ISP and microdialysis monitoring: Although routine standard-of-care measures will be taken to prevent surgical-site infection, the presence of indwelling cathethers / probes is associated with an additional risk of infection (estimated at 1%). As per standard-of-care guidelines, all participants will be closely monitored for any signs of systemic or surgical-site infection during the post-operative period in the neurosurgical ICU and following transfer to progressive care.

Blood draw: Blood samples will be taken during the study. Using a needle to remove blood from a vein. It may be necessary to try more than once to draw blood. Participants might feel pain or be light-headed from this and may have the following at the site of the needle stick when blood is drawn:

- Additional bleeding at the site of the blood draw
- Temporary discomfort
- Bruising
- Infection (rarely)

Sural nerve graft harvesting procedures. The surgical risk is minimal and this part of the protocol is considered a minor surgery and employs a surgical approach that is used for sural nerve biopsies. The incision is ~3cm in length located above and behind the lateral aspect of the ankle. The sural nerve is a sensory nerve that supplies sensation to the lateral aspect of foot and heel. Participants in previous studies have reported either a temporary sensory loss or permanent loss of sensation to a small dermatomal patch on the outer aspect of the foot and/or heel. For this participant population, this would not be a concern. Although this study does involve grafting, participants will donate their own tissue. This eliminates the risk of graft rejection and obviates the need for immunosuppressant medications typically used with other transplant studies.

Magnetic Resonance Imaging (MRI): The MRI may be with or without contrast agent and participants may notice discomfort, tingling or warmth in the lips, metallic taste in the mouth, tingling in the arm, nausea, or headache. These symptoms go away quickly. There is also a small risk of an allergic reaction to the contrast agent.

Sedation (Diazepam): Respiratory depression, Suicidality, Dependency and abuse, Bradycardia, Hypotension, Syncope, Depression, Anterograde amnesia, Headache, Nausea, Tremor, Dystonia

Genetic or genomic testing is possible: Even without the participant's name or identifiers, genetic information is unique to them. The results of genetic research apply to both the participant and their family members. Genetic information used improperly to discriminate or support negative stereotypes could cause the participant their family distress. The researchers do not know whether future technology will make it possible for someone to trace the participant's genetic information back to them.

There may be additional risks associated with banking specimen samples such as the risks associated with blood draws and the potential for a breach of confidentiality.

Social Risks: Breach of confidentiality could impact insurability, employability, reproduction plans, family relationships, immigration status, paternity suits, and stigmatization, if applicable.

There is a federal law called the Genetic Information Nondiscrimination Act (GINA). Generally, GINA makes it illegal for health insurance companies, group health plans, and most employers to discriminate against a person based on their genetic information. Be aware that GINA does not protect the participant against discrimination by companies that sell life insurance, disability insurance, or long-term care insurance. It also does not prohibit discrimination on the basis of an already known genetic disease.

There is no guarantee that the subjects will receive any benefit from taking part in this study.

Safety Precautions: Provisions to guard against the potential risks and discomforts above are as follows: Every precaution to prevent a direct study injury will be taken by medical personnel and the investigators. The research participant will be followed by physicians, fellows, registered nurses and other research staff members for the duration of the participant's participation. Routine care can be provided by the hospital staff.

Emergency medical equipment, medications and supplies will be at the physician's disposal should the participants have an acute untoward reaction. The participants will be monitored for clinical adverse experiences throughout study therapy.

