#### Please consider these resources: NIH Diversity Policy

#### FDA Diversity Guidance

Number of Participants: To assess the feasibility of recruitment and of the protocol procedures (specifically the = 48 hours injury-to procedure timeframe), the study will plan to enroll and treat 10 patients.

All participants with American Spinal Injury Association (ASIA) impairment scale A or B acute traumatic spinal cord injuries will be assessed for suitability and prospectively enrolled in the study. Either cervical (C2-C8) or thoracic (T1-T12) level injuries in participants aged 18 to 80 years old will be included. Detailed eligibility criteria are listed below.

The use of immunosuppressive therapy (including methylprednisolone and other corticosteroids) will be discouraged; however, use of such therapy will not require exclusion or discontinuation from the study. Of note, the recent Riluzole study reported that corticosteroids were administered at the time of admission to only ~30% of the patients (while 58% of historic NACTN registry patients had received this treatment).[15, 16]

Inclusion Criteria:

- 1. Age: = 18 years and = 80 years
- 2. Written informed consent by patient or legal authorized representative
- 3. No other life-threatening injury
- 4. No evidence of sepsis
- 5. Acute cervical or thoracic SCI with ASIA Impairment Scale grade A or B on admission
- 6. Non-penetrating SCI at neurologic level from C2 to C8 or T1 to T12
- 7. The ability to undergo surgical intervention including study procedures through a posterior approach within 48 hours of injury

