Fortuitously, neurosurgery and neuroscience colleagues at the University of Kentucky have already established and validated a reproducible source of cellular tissue from the peripheral nervous system,[8, 9] that contain injured-peripheral nerve tissues shown to include a variety of cells that express several key growth factors and repair molecules including glial cell line-derived neurotrophic factor, brain-derived neurotrophic factor, nerve growth factor, and neurotrophin-3. They have implanted ANGI in to the CNS of 80 participants without any serious adverse events related to the study intervention and with the most common study-related adverse event being paresthesias and acute pain at the lateral aspect of the foot and ankle ipsilateral to the biopsy. Amongst other possible cellular neurotrophic sources 9 contained within these grafts, Schwann cells are known to transdifferentiate after injury into an activated repair phenotype through a c-Jun mediated pathway and produce a host of repair and survival promoting neurotrophins and anti-apoptotic factors.[28]

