## Study Design

Describe and explain the study design (e.g., observational, secondary analysis, single/double blind, parallel, crossover, deception, etc.).

- Clinical Research: Indicate whether subjects will be randomized and whether subjects will receive any placebo.
- Community-Based Participatory Research: If you are conducting community-based participatory research (CBPR), describe strategies for involvement of community members in the design and implementation of the study, and dissemination of results from the study.
- Qualitative research: Indicate ranges where flexibility is needed, if a fixed interview transcript is not available, describe interview topics including the most sensitive potential questions.
- Research Repositories: If the purpose of this submission is to establish a Research Repository (bank, registry) and the material you plan to collect is already available from a commercial supplier, clinical lab, or established IRB approved research repository, provide scientific justification for establishing an additional repository collecting duplicate material. Describe the repository design and operating procedures. For relevant information to include, see the UK Research Biospecimen Bank Guidance or the UK Research Registry Guidance.

This is a double-blind, 12-month pilot study to evaluate of the safety, feasibility, and preliminary efficacy of dorsal myelotomy and expansive duraplasty performed either without or with autologous nerve graft implantation after acute traumatic spinal cord injury. Ten participants will be allocated to receive either DMED (n=5) or DMED + ANGI (n=5) based on a block design. Participants and assessors will be blinded to group allocation. Excess sural nerve samples will be collected for banking/analysis (may include proteomic, culturing, genomic, cellular analysis).

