- · Spinal cord injury (SCI) Time, Cause, and Level of injury
- Demographics and Clinical Variables (age, race, gender, and body mass index (BMI)
- Neurological examination including ISNCSCI motor and sensory assessments
- ECG (12-lead)
- · Clinical laboratory tests (complete blood count, chemistry, liver function tests)

Eligible participants will be enrolled and undergo study procedures within the first 48 hours after documented SCI. This injury-toprocedure timeframe appears feasible given the injury-to-admission times reported in recent SCI studies. For instance, in the phase 3 Riluzole study, 94.6% underwent surgical decompression within 24 hours, which was typically preceded by completion of CT and MRI studies.[16]

Study-related Management (standard-of-care) :

• Serial vital signs (temperature, blood pressure, pulse, respiration rate, O2 saturation) and

neurologic (International Standards for Neurological Classification of Spinal Cord Injury - ISNCSCI) assessments

• Blood work; CT scans of the spine and head (as indicated); pre- and post-operative MRI of the cervical/thoracic spine

Cervical / thoracic CT studies will reveal the nature of the associated spinal fracture and/or misalignment. Acute SCI management guidelines, most recently revised by a consensus panel in 2013[14], will be adhered to. These guidelines include avoidance of hypoxia and hypotension with induced hypertension as needed to keep mean arterial pressure = 85mmHg for 7 days. The ability to undergo early surgical intervention, which is increasingly recognized as a standard-of-care intervention,[2] constitutes an inclusion criterion for the study.

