Surgical Protocol: All subjects will undergo spinal cord decompression and instrumented spinal stabilization through a posterior approach according to standard-of-care guidelines in place at the Department of Neurosurgery, University of Kentucky. The extent of laminectomies will be based on the extent of cord edema as noted on the pre-operating MRI study. All patients will also undergo dorsal myelotomy and expansive duraplasty (DMED) under microscopic magnification. The dorsal dura will be incised longitudinally in the midline with the length once again estimated from the length of the spinal cord edema on the pre-operative MRI. Under high microscopic magnification, the dorsal midline of the spinal cord will be identified to allow for a myelotomy using a microsurgical beaver-blade extending through to the anteroposterior midline. While no attempt will be made to suction or otherwise excise intramedullary spinal cord hematoma, it is understood that spontaneous egress of variable amounts of clotted blood may be noted given the severity of the trauma typically noted in some patients. Following probe insertion (see below), we will then suture an appropriately-sized elliptical patch of artificial dura (e.g., Durepair, Medtronic, Minneapolis, MN) to the dural edges to expand the intradural space. The duraplasty will be supplemented with a patch of fibrin glue (e.g., Tisseel, Baxter, Deerfield, IL).

A total of n = 5 patients will undergo supplemental ANGI procedure in addition to DMED. Once the dorsal myelotomy is completed, the sural nerve will be accessed through a standard neurosurgical approach as employed for biopsy of the sural nerve. A 4 cm incision will

be fashioned starting above the lateral epicondyle and an approximately 2 cm section of the nerve will be excised, placed in normal saline, and appropriately trimmed. Under direct high-magnification microscopic visualization, an approximately 3-5 mm segment (cut into smaller, 0.5 to 1mm segments) of sural nerve/fascicles will be carefully deposited over the dorsal myelotomy site. Great care will be taken to ensure that the subsequent duraplasty is expansive enough such that no additional compressive effect is associated with the ANGI procedure.

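### The protocol dismisses lasting sensory loss from the sural nerve harvest although AIS B patients are eligible, and its visit schedule would miss non-serious donor-site harm first noticed after Day 42

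*Protocol*

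**What the plan says.** In the Protocol, Potential Risks & Benefits, the paragraph on sural nerve harvesting states that "The sural nerve is a sensory nerve that supplies sensation to the lateral aspect of foot and heel". It reports that earlier participants had either temporary sensory loss or "permanent loss of sensation to a small dermatomal patch on the outer aspect of the foot and/or heel", and closes the matter with "For this participant population, this would not be a concern".

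Other parts of the protocol bear on that sentence:

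- **Eligibility** (Study Population, Inclusion Criteria, item 5): "Acute cervical or thoracic SCI with ASIA Impairment Scale grade A or B on admission". There is no limit on the share of grade B.
- **Aim** (Background): DMED (dorsal myelotomy and expansive duraplasty) and cell-based therapy such as ANGI are presented as candidates for improving functional recovery.
- **Earlier experience** (Background): among 80 people who received this type of graft in the central nervous system, the most common study-related adverse event was "paresthesias and acute pain at the lateral aspect of the foot and ankle ipsilateral to the biopsy".
- **Who is exposed** (Research Procedures, Surgical Protocol): "A total of n = 5 patients will undergo supplemental ANGI procedure in addition to DMED". The harvest is described for these participants only. Study Design gives the split: "Ten participants will be allocated to receive either DMED (n=5) or DMED + ANGI (n=5) based on a block design".
- **Safety recording** (Objectives, Specific Aim 1): adverse events are assessed during the hospital stay through Day 28. The follow-up list in Research Procedures records additional adverse events of any kind at Days 28 and 42. At Days 84, 182 and 365 it records additional serious events only, alongside review of events still unresolved.

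**The concern.** The dismissal makes sense only if nobody in the trial can feel the outer foot, now or later. The protocol's own eligibility and purpose say otherwise. By the standard definition of the grade, which the protocol does not spell out, an AIS B participant has some sensation below the injury. For such a person who can feel the patch, the harvest can create a new deficit. For someone without sensation there at surgery, the deficit or any pain can become noticeable only if sensation returns, which may be months later.

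That timing is where the recording rules are weakest. Donor-site numbness, tingling or pain would usually be non-serious, and from Day 84 the schedule asks only for new serious events. The harm most specific to ANGI could thus be under-counted in the one arm that carries it. Safety of DMED without and with ANGI is Specific Aim 1, so the loss falls on a main purpose of the study.

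**Working it through.** The protocol gives no rate, power or margin on this point, so there is no stated figure to reproduce. The allocation adds up: 5 + 5 = 10.

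**Step 1. Does the dismissal fit the population?** The sentence rests on the population alone. The inclusion criteria admit grades A and B. The share of grade B is not fixed, so anywhere from 0 to 5 of the five ANGI participants may be grade B. Preserved sensation somewhere below the injury does not prove sensation at the outer foot, but it removes the basis for a blanket statement. The dismissal also sits badly with the stated hope of recovery.

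**Step 2. Does it fit the earlier experience?** The Background puts paresthesia and acute pain at the outer foot and ankle first among study-related adverse events. The harvest paragraph mentions neither. It dismisses loss of sensation, which is a different event at the same site. The same section estimates other risks: bleeding below 1%, spinal fluid leak 5%, catheter infection 1%. The form's instructions ask for the seriousness and likelihood of each risk, but none is estimated for sensory loss.

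**Step 3. When can a new non-serious event be recorded?**

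| Visit | New non-serious AE | New serious AE | Earlier unresolved AE |
|---|---|---|---|
| Day 28 (± 7) | yes | yes | yes |
| Day 42 (± 7) | yes | yes | yes |
| Day 84 (± 14) | not listed | yes | yes |
| Day 182 (± 14) | not listed | yes | yes |
| Day 365 (± 30) | not listed | yes | yes |

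Nominal time without a listed place for a new non-serious event: (365 − 42)/365 = 323/365 = 88%. Under the Day 28 limit in Specific Aim 1: (365 − 28)/365 = 337/365 = 92%.

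**Step 4. What does one missed event weigh?** With five exposed participants, one uncounted case changes the observed ANGI incidence by 1/5 = 20 percentage points. The number likely to be missed cannot be estimated, because the protocol gives neither the rate of lasting loss nor the share of grade B.

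**Step 5. Could the harvest also shift a sensory score?** Screening includes "Neurological examination including ISNCSCI motor and sensory assessments", and the ASIA-ISCOS worksheet is a study data form, but it is not shown. Assume its standard layout: one scored point at the lateral heel on each side, light touch 0–2 plus pin prick 0–2, total 224. One affected participant then loses at most 2 + 2 = 4 points. If k of five ANGI participants had full sensation there and lost both modalities, the arm mean falls by 4 × k/5:

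| k | Fall in ANGI mean | Share of 224 |
|---|---|---|
| 0 | 0 | 0% |
| 1 | 0.8 | 0.36% |
| 2 | 1.6 | 0.71% |
| 3 | 2.4 | 1.07% |
| 4 | 3.2 | 1.43% |
| 5 | 4.0 | 1.79% |

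The range runs from zero to 1.8% of the scale, and nothing in the protocol selects a value within it.

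**The case against.** The strongest reply is that the sentence describes a risk and is not a recording rule. Data and Safety Monitoring calls for real-time monitoring of adverse events, grading, attribution to DMED with or without ANGI, and a summary of all events. Research Procedures also says in general terms that adverse events are followed to one year. A deficit recorded by the Day 42 visit would be reviewed at each later one. The dismissed event is sensory loss, whereas the common event in the Background is paresthesia and pain.

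Much of this stands. Early events should be captured, and the dismissal does not extend to pain or paresthesia. But the general statements do not match the visit list or the Day 28 limit in Specific Aim 1, and the visit list is what staff will follow. An event that first appears after Day 42 has no listed place unless it is serious. The attribution rule adds to this: investigators are to weigh complications expected in spinal cord injury anyway, so foot numbness is easily called unrelated.

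A reader might infer more: that the harvest biases the trial's sensory outcome against ANGI, so that sensory points at the heel should be dropped in both arms. The documents do not support this. No sensory score is named as an outcome. Objectives names motor scores for the hospital stay, the later visits use AIS grade and the Spinal Cord Independence Measure, and Data and Safety Monitoring speaks of motor scores and functional outcomes. None of these is shown to be altered by a small numb patch. That the patch contains a scored point depends on a worksheet not shown, the reported loss may spare the heel, and the shift may be zero.

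Nor can one say that participants are not told of the risk, since the consent form is not available here.

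**Conclusion.** The concern holds as a fault in the risk statement with a consequence for safety capture. The dismissal is unsupported for AIS B participants and for anyone who regains sensation, and it must be reconciled with the inclusion criteria and the Background. Under the visit schedule, non-serious donor-site harm first noticed after Day 42 can be missed for about 88% of the nominal year, in the only arm exposed to it; each missed case is worth 20 percentage points of incidence with n = 5.

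This rests on the usual meaning of AIS B and on staff following the visit list as written. How many events would be missed is unknown. An effect on a sensory score is a side issue: conditional on sensory scores being compared between arms, and at most about 4 points per affected participant under the assumed worksheet layout.

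**What to change.** 1. Delete the dismissing sentence. State the risk of temporary or permanent sensory loss, together with paresthesia and pain, consistently with the inclusion criteria and the Background.
2. Record donor-site sensory loss, paresthesia and pain as adverse events at every visit to Day 365, serious or not. Ask the same questions in both arms, through someone other than the blinded assessors, and keep the answers from those assessors.
3. Align the statements on how long adverse events are recorded: Day 28 in Specific Aim 1, Day 42 in the visit list, and one year in the general text.
4. Record the harvest side in a field the blinded assessors cannot see. If ISNCSCI sensory scores are ever compared between arms, flag the outer foot/heel point on that side as possibly affected by a non-spinal cause. Keep the corresponding data in the DMED arm.

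The cost is a few added questions per visit, one data field and some wording. The sample size, visits and named outcomes do not change.
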